5.0 CRITERIA FOR SUBJECT ELIGIBILITY

All Caucasian and African-American men attending both the Department of Urology, New York Presbyterian Hospital, Weill Medical College of Cornell University, Manhattan, the Department of Urology, SUNY Downstate Medical Center, Brooklyn, and the Department of Urology, Kings County Hospital, who are to undergo a prostate biopsy because of suspicion of having prostate cancer are eligible for enrollment in this protocol. All patients will proceed with their planned intervention as part of their standard therapy. Serum/plasma samples will be obtained before their intervention, at the same time as samples that are part of routine care.

5.1 Subject Inclusion Criteria

- Men aged 18 years or older
- Have a PSA level between 2 and 10 ng/ml
- May or may not have an abnormal digital rectal examination
- Scheduled for trans-rectal ultrasound (TRUS) guided systematic prostate biopsy as part of routine medical care. All sites (Department of Urology at SUNY Downstate Medical Center, Brooklyn, the Department of Urology, New York Presbyterian Hospital, Weill Medical College of Cornell University, Manhattan and the Department of Urology, Kings County Hospital,) will perform a standardized 14 core biopsy protocol.
- Signed, informed consent
- Patient must be able to attend the pre-biopsy blood draw

5.2 Subject Exclusion Criteria

- Any period of prior/current treatment with hormonal therapy (LHRH agonist/antagonist, antiandrogen, 5-alpha-reductase inhibitor)
- Prior pelvic radiation
- A period of less than 6 months prior/current treatment with an alpha-blocker
- Previous diagnosis of prostate cancer

6.0 RECRUITMENT PLAN

Patients will be recruited from the Urology Clinic at Department of Urology, SUNY Downstate Medical Center in Brooklyn, the Department of Urology, New York Presbyterian Hospital, Weill Medical College of Cornell University, Manhattan and from Department of Urology, Kings County Hospital,. We will prospectively enroll 500 patients in total, 250 African-American and 250 Caucasian patients referred to both hospitals for TRUS guided

IRB
PB

Amended: 2/1/12

Memorial Sloan-Kettering Cancer Center IRB Protocol

IRB#: 08-114 A(4)

prostate biopsy. Approximately 30% will be found to have histological evidence of prostate cancer on their biopsy (150 patients) and 70% (350 patients) will not. This is based on approximately 33% expected to be positive in the African-American samples³ and 25-30% expected to be positive in the Caucasian samples. We anticipate that accrual will be completed in two years.

Estimated breakdown of target population by race/ethnicity:

% Native American/Alaskan	0%
% Asian/Pacific Islander	0%
% Black Non-Hispanic	50%
% Hispanic	0%
% White Non-Hispanic	50%
% Other	0%

It is stated that taking part in this study is voluntary and patients have the right to withdraw at any time. Participation in the study will not have an impact on the clinical care patients receive.

7.0 ASSESSMENT/EVALUATION PLAN

Patients referred for prostate biopsy as part of their routine care are to be recruited. Patients will undergo standard medical evaluation/care by undergoing a prostate biopsy because of an elevated PSA blood test and/or an abnormal digital rectal prostate examination. The protocol involves obtaining the research blood sample at the time of routine pre-biopsy blood draw. As such, an extra five (40 mL) tubes of blood will be drawn. The serum specimens obtained will be utilized for proteomic profiling comprising MALDI-TOF MS, and serum biomarker assays.

Routine histological examination of the tissue specimens is considered standard care and not research.

8.0 TOXICITIES/SIDE EFFECTS

Patients participating in this study will be at risk for having prostate cancer. The risks and benefits of any procedures including prostate biopsy will not be altered by participation in this protocol. The plan is to obtain the research blood sample at the time of routine pre-biopsy blood draw. As such, the extra five (40 mL) tubes of blood should result in no adverse effects to the patient. If, however, the patient requires a separate blood sample to be drawn, this may result in momentary pain and possible bruising at the site where blood was drawn. There is a small risk of bruising or fainting with phlebotomy. Rarely, an infection may develop at the site from which blood is drawn.

IRB
PB

Amended: 2/1/12

Memorial Sloan-Kettering Cancer Center IRB Protocol

IRB#: 08-114 A(4)

9.0 PRIMARY OUTCOMES

See section 4.0

10.0 CRITERIA FOR REMOVAL FROM STUDY

If at anytime the patient is found to be ineligible for the protocol as designated in the section on Criteria for Patient/Subject Eligibility (i.e., a change in diagnosis), the patient will be removed from the study.

If the patient withdraws consent, refuses to provide research blood sample, or does not undergo scheduled trans-rectal ultrasound (TRUS) guided systematic prostate biopsies, the patient will be removed for the study.

11.0 BIOSTATISTICS

This is a prospective, serum proteomics study of men who are to undergo prostate biopsy. The purpose is to determine if proteomic profiles can be used to distinguish between men with prostate cancer on biopsy from men with no cancer on biopsy. Overall, 500 men will be part of the study. Based on previous experience, about 30% (150 patients) will have cancer and about 70% (350 patients) will not. Accrual is expected to take two years.

An initial biopsy will be undertaken for these patients because of a suspicion of prostate cancer. Because there is about a 20% false negative rate on a single biopsy, and a negligible false positive rate, a second biopsy will be recommended at six months only for those who are negative on the first biopsy. Patients who are positive on the first or second biopsy will be assigned to the “cancer” group, while those who are negative for all their biopsies will be assigned to the “no cancer” group. Assuming the two biopsies can be treated as independent, there would be about 4% that should be in the “cancer” group that would be assigned to the “no cancer” group if all those negative on the first biopsy got the second biopsy. We believe that over 90% of the patients that are negative on the first biopsy will get the second biopsy, leading to an expected false negative rate of 5 to 6%. Since the number incorrectly assigned should be small, we ignore it in the calculations below.

The data from each proteomic study is a two-dimensional plot of mass over charge (m/z) and intensity. The intensity at a particular m/z is proportional to the amount of the peptide with that particular molecular weight in the sample. The m/z values are continuous, but as a first step, these values will be reduced to a finite set of “bins” based on intensity “peaks” across samples, as previously described.¹² To prevent against bias, the bins and the intensities at each bin will be computed while blinded to disease status. The value for each m/z bin for each

**IRB
PB**

Amended: 2/1/12

Memorial Sloan-Kettering Cancer Center IRB Protocol

IRB#: 08-114 A(4)

sample will be analyzed in two ways. One way will be to use the actual intensity measure, while the other way will be to convert it to a binary (absence or presence) value.

Primary Objectives:

Prediction models for “cancer” or “no cancer” membership will be developed. The first 250 patients accrued will be used as a training set and the second 250 will be used as a validation set. As the optimal analysis methods for these types of experiments are undefined, at least three approaches will be evaluated. One simple approach that will be used is to build a score for each patient based on forward stepwise logistic regression. The second method that will be used involves a statistical technique called “boosting” that puts extra emphasis on correct assignment of difficult cases. This approach was shown to be useful in the analysis of proteomic data in an earlier study.¹⁶ This will be combined with a logistic regression approach. A third technique that will be used is called “logic regression”.¹⁷ Here, a search is made through a large subset of the many possible combinations of binary predictors (in this case bins) to build a good prediction rule. This will be straightforward when the data is binary, but it can be utilized for continuous data by setting optimal thresholds for the intensities. In Aim 2, proteomic data will be combined with known biomarkers (PSA and hK2) and compared to models with just the biomarkers. Therefore, for this analysis, the known biomarkers will be forced into models; for Aim 1, only proteomic data will be included. To prevent over-fitting of the training set, 10-fold cross-validation will be utilized in the modeling. The modeling results will be evaluated using the area under the ROC curve (AUC), and the best models will be validated on the validation set. Models will be constructed both with and without clinical variables such as age and family history.

Sample size considerations for the prediction rules are based on the AUC. The methods used here were introduced by Pepe.¹⁸ Since the known biomarkers, such as PSA, give an AUC of approximately 0.8, our goal in Aim 1 is a prediction rule with an AUC of greater than 0.8. For the validation set of size 250, fixing the type I error rate at 0.05, the true AUC would have to be at least 0.86 to have at least 80% power. This is based on a one sample test. In Aim 2, we are comparing the AUC of combining the standard biomarkers with proteomic data to just using the biomarkers. In this case, the AUC of the biomarkers plus proteomic model would have to be at least 0.89 to have at least 80% power. This is a two sample test. While the data are paired, we follow Pepe’s recommendation¹⁸ to treat the samples as independent for sample size determination because the correlation is unknown without pilot data and treating the samples as independent is conservative.

In addition to prediction, the association between peak intensity and group membership (“cancer” vs. “no cancer”) will be evaluated for every bin using the Wilcoxon rank sum test or Fisher’s exact test, depending on whether the data is being treated as continuous or binary. Adjustment will be made for multiple comparisons using the false discovery rate methods of Benjamini and Hochberg.¹⁹ Finally, the data will be hierarchically clustered to examine whether there are distinct peptide patterns associated with subsets of samples.

IRB
PB

Amended: 2/1/12

Memorial Sloan-Kettering Cancer Center IRB Protocol

IRB#: 08-114 A(4)

The full set of 500 samples will be examined using the standard MALDI technique at MSKCC. Thus, the main prediction rules that will be reported will be for these samples using this method at this site. As there are three time points, three separate rules will need to be reported and compared as discussed below. In addition, all data sets will be simultaneously processed in order to get the same sets of bins for reproducibility comparisons. Two other MALDI methods and two LC-MS methods will be used on a subset. For each, the same subset of 100 malignant samples and 100 benign samples will be examined. The same analyses as on the full set will be undertaken, but here 50 of each will be used as a training set and 50 of each will be used as a test set.

Secondary Objectives:

The proteomic profiles of Caucasian men and of African-American men will be compared to see if the same peaks that are predictive in one are predictive in the other. In addition, the AUCs for the two groups will be compared based on models that use all the data.²⁰ Finally, separate models will be built for the two groups and the AUCs will again be compared.

As mentioned in section 4, we distinguish two aspects of reproducibility: *analytical* reproducibility, that is, whether a proteomics machine produces similar peaks on repeated samples, and *inferential* reproducibility, whether a proteomics experiment produces similar conclusions when repeated.

The basic method for assessing analytic reproducibility will be through the concordance correlation coefficient (CCC)²¹ of the intensity estimates. This CCC is a measure of the agreement between two readings of the same sample via the variation from the 45 degree line through the origin. It is on the same -1 to 1 scale as the standard Pearson correlation. Since there are about 600 bins per sample, there will be 600 CCCs for every comparison. Therefore, we will compute summary statistics of the CCCs. These summaries will be based on all the bins and just the discriminating bins. Since the statistic is only pair-wise, different analyses will have to be done for the three time points, the two sites, and the two platforms (MALDI and LC-MS). The only comparison between the platforms will be between standard MALDI and standard LC-MS.

Inferential reproducibility will consist of two components: determination of whether the same peaks are discriminating and comparisons of the AUCs for the prediction of cancer or no cancer. These comparisons will be made for the same varying conditions as for analytic reproducibility. For the former, discriminating peaks will be identified using a variety of thresholds and the differences will be reported as summary statistics. For the latter, formal testing of differences in AUCs will be undertaken, as well as summary statistics. A question of particular interest will be whether the difference in the estimated AUC from the two sites using the standard MALDI platform is statistically significant.

IRB
PB

Amended: 2/1/12

Memorial Sloan-Kettering Cancer Center IRB Protocol

IRB#: 08-114 A(4)

The last two secondary aims involve collection of material for future studies and no current data analyses.

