1.0 PROTOCOL SUMMARY AND/OR SCHEMA

Current recommendations suggest that all men over the age of 50 years should have annual prostate cancer screening with serum PSA measurement and digital rectal examination. Men with an abnormal examination and/or an elevated PSA test are generally referred for a prostate biopsy. Not all men with an elevated PSA have prostate cancer. Positive biopsy rates in a screened population will be in the order of 25-40%.^{1,2} A recent study demonstrated a positive prostate biopsy rate for African American men with an elevated PSA and/or abnormal DRE to be 33%.³

Incidence rates of prostate cancer for African-Americans are among the highest in the world. Men of African descent have a 60 percent higher risk of developing prostate cancer than Caucasian men and have twice the risk of dying from it.⁴ Furthermore, African American men have higher levels of testosterone, which may contribute to higher serum PSA levels, worse Gleason scores, and more advanced stage of disease at diagnosis. The increased risk of advanced stage disease persists in African-American men, even after adjustment for socioeconomic, educational, and clinical variables. The patient population of SUNY Downstate Medical Center, Brooklyn offers a unique opportunity to recruit a large number of African-American men. The patient population at New York Presbyterian Hospital, Weill Medical College of Cornell University, Manhattan offers the opportunity to recruit a large Caucasian population. The patient population attending MSKCC predominately have a diagnosis of prostate cancer already on their first attendance and hence are unsuitable for this study.

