4.0 OVERVIEW OF STUDY DESIGN/INTERVENTION

4.1 Design

This study will enroll two groups of 250 patients who are to undergo prostatic biopsy as part of their routine medical care because of suspicion of prostate cancer (elevated PSA between 2 and 10 ng/ml, abnormal rectal examination, or both). The first group will contain 250 patients of African-American descent and the second will contain 250 Caucasian men. The patients (both African American and Caucasian) will be recruited at both centres - New York Presbyterian Hospital, Weill Medical College of Cornell University, Manhattan and SUNY Downstate Medical Center in Brooklyn.

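### Training and validation sets are cut by combined accrual order while two race quotas fill, so race mix is uncontrolled and any imbalance in one set is mirrored in the other

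*Combined protocol and SAP*

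**What the plan says.** Section 11.0 (Primary Objectives) gives one allocation rule for the full cohort: "The first 250 patients accrued will be used as a training set and the second 250 will be used as a validation set". The rule uses position in the combined accrual list and nothing else.

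Section 4.1 sets the composition of the cohort: "The first group will contain 250 patients of African-American descent and the second will contain 250 Caucasian men". Section 6.0 repeats it: "We will prospectively enroll 500 patients in total, 250 African-American and 250 Caucasian patients".

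On where the men come from, Section 1.0 says that "SUNY Downstate Medical Center, Brooklyn offers a unique opportunity to recruit a large number of African-American men" and that the Manhattan hospital "offers the opportunity to recruit a large Caucasian population". Section 4.1 adds that both races will be recruited at both centres. Section 11.0 gives only a total duration ("Accrual is expected to take two years"). No accrual rate by race or by site appears.

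Race is not a listed model covariate; the clinical variables named as examples are age and family history. No section paces enrolment by race or stratifies the split by race or site.

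Under Secondary Objectives, AUCs are compared between the races in two ways: from models using all the data, and then "separate models will be built for the two groups and the AUCs will again be compared". The text does not say whether either comparison uses the 250/250 split.

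**The concern.** With two fixed quotas and one cut in the combined list, the two sets have the same race mix only if both races enrol at about the same speed. Otherwise the faster race is over-represented in training and the slower race, to the same extent, in validation.

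Two results could be affected.

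- **Primary objectives.** If some discriminating peaks are race-specific, a rule learned mostly in one race is tested mostly in the other. A lower validated AUC could then reflect race mix rather than weak signal. The protocol treats this as open, since a secondary objective asks whether profiles differ by race.
- **Race comparison.** If the separate models follow the same split, one is trained on far fewer cancers than the other. Its AUC will be lower for that reason alone, and the gap could be read as biology.

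**Working it through.** **1. The plan's own figures.** Section 11.0 expects that "about 30% (150 patients) will have cancer and about 70% (350 patients) will not", so a validation set of 250 holds about 75 cancers and 175 non-cancers. For Aim 1 (null AUC 0.80, type I error 0.05) the plan says a true AUC of 0.86 is needed for 80% power; for Aim 2, 0.89.

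Use the Mann-Whitney variance under an equal-variance binormal model:

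Var(A) = [A(1−A) + (n1 + n0 − 2)(Q − A²)] / (n1·n0), with Q = Φ₂(Φ⁻¹(A), Φ⁻¹(A); ρ = 0.5).

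Take a one-sided 0.05 test (the plan does not state sidedness): power = Φ((A − 0.80)/SE − 1.645).

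- Aim 1: at A = 0.862, Q = 0.7752 and SE = 0.0248, so power is 80.3%. At exactly 0.86 it is 77.4%.
- Aim 2, two independent samples: at 0.8925 the combined SE is 0.0370 and power is 80.3%. At exactly 0.89 it is 78.1%.

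To two decimals these match the plan's 0.86 and 0.89. Starting from 0.862, a loss of 0.01 in true validated AUC lowers Aim 1 power to 64.5%, and a loss of 0.02 lowers it to 47.1%.

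**2. Race mix at patient 250.** Let r be the accrual rate of the faster race divided by that of the slower (assumed). The faster race contributes 250r/(1+r) men to training. Validation is the mirror image because each quota totals 250.

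| r | Training, faster/slower | Validation, faster/slower |
|---|---|---|
| 1 | 125/125 expected; 95% chance range 114–136 of either race | mirror |
| 1.5 | 150/100 | 100/150 |
| 2 | 167/83 | 83/167 |
| 3 | 188/62 | 62/188 |

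At r = 2 the faster quota closes at patient 250 + 125 = 375, so the last 125 men, half the validation set, are all of one race.

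Cancers in training at r = 3, using 33% for African-American men and 27.5% (midpoint of 25–30%) for Caucasian men, both from Section 6.0: slower race 62.5 × 0.275 to 62.5 × 0.33 = 17 to 21; faster race 187.5 × 0.275 to 187.5 × 0.33 = 52 to 62.

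**3. Effect on AUC: two illustrative simulations.** Both train on the first 250 and test on the mirror-image second 250, with 600 bins (Section 11.0 says about 600). Effect sizes and accrual ratios are assumptions.

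- Simulation A: 300 runs, 0.6 SD effects, mean-difference score on the top 20 bins, prevalence 33%/27.5%. The A rows marked * come from a repeat with ten informative bins, which closely reproduces its other results.
- Simulation B: 400 runs, 8 true peaks per race with ideal AUC 0.90 in both races, logistic model on the top 10 bins, prevalence 30%.

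Pooled rule, validated AUC:

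| Scenario | 1:1 | 2:1 | 3:1 |
|---|---|---|---|
| Half the signal race-specific, A | 0.789 | 0.780 | 0.767 |
| Half race-specific, B | 0.796 | 0.777 | 0.770 |
| Quarter race-specific, B | 0.837 | 0.832 | 0.827 |
| All peaks shared, A* | 0.870 | 0.866 | 0.865 |
| All peaks shared, B | 0.870 | 0.872 | 0.871 |

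The loss with half the signal race-specific is 0.009 to 0.019 at 2:1 and 0.022 to 0.026 at 3:1. Adding a race difference of 0.3 in mean bin level to the shared case in B gave 0.871, 0.870 and 0.862.

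Separate models trained within the split, all peaks shared (faster vs slower race):

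| Ratio | A | B |
|---|---|---|
| 1:1 | 0.80 vs 0.79 | 0.801 vs 0.797 |
| 1.5:1 | not run | 0.826 vs 0.762 (gap 0.064) |
| 2:1 | 0.84 vs 0.72 (gap 0.12) | 0.840 vs 0.718 (gap 0.122) |
| 3:1 | 0.85 vs 0.68 (gap 0.17) | 0.857 vs 0.679 (gap 0.177) |

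**4. The same comparisons without the split.** With each race's model built on all 250 of its men and cross-validated, the 3:1 gap vanishes (0.86 vs 0.86, A*). A pooled model cross-validated on all 500 men gives a race difference of −0.001 (B, half race-specific).

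**5. With the split balanced by race.** At 125 + 125 in each set, B gives race differences of −0.001 to +0.003 (pooled model) and −0.006 to +0.004 (separate models).

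**The case against.** A prespecified split in time is a legitimate validation design, and several facts limit the harm.

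- **Unequal accrual is not shown.** A reader might infer from Section 1.0 that each race comes from its own hospital at its own pace. Section 4.1 has both races recruited at both centres, and different sources need not mean different speeds. A 3:1 ratio would have one quota full in about 8 of the planned 24 months; nothing in the documents points to that.
- **The primary-aim loss needs two conditions together:** unequal accrual and race-specific peaks. Even then it is small beside sampling error: near an AUC of 0.79 with 75/175 men the standard error is about 0.034 (Hanley-McNeil).
- **The large gaps rest on a reading of the secondary objective.** The split sentence stands under Primary Objectives. The race comparisons do not refer to it, and the phrase about models using all the data may mean all 500 men.
- **The simulated models are simple stand-ins.** They are not the stepwise, boosting or logic regression methods that the plan names.

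All of this stands, and it limits size and confidence. It does not remove the gap: the accrual-order rule is the only train/validate rule for the full cohort, it leaves race mix to chance and logistics, and balancing by race keeps the time order within each race.

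**Conclusion.** The split leaves race mix uncontrolled, and the mirror-image imbalance follows by arithmetic from the two quotas. Its consequences are conditional.

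- **Primary objectives:** a loss of about 0.01 to 0.03 in pooled validated AUC if accrual is between 2:1 and 3:1 and half the signal is race-specific. The loss is smaller with a quarter race-specific (0.005 to 0.010), and essentially nil with equal accrual or fully shared peaks. A loss of 0.01 to 0.02 would matter if the true AUC sat at the plan's target, where power has no slack.
- **Race comparison:** a false difference of about 0.12 (2:1) to 0.17–0.18 (3:1) from the separate models, but only if they are trained and tested within this split.

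A reader might infer that the plan will produce a false race difference, or that its primary rule will be validated mainly in the other race. The documents do not support either: they give no accrual rates by race and do not name the data set for the race models. The simulated sizes are illustrations, not predictions. This is a cheap improvement to the design, held with moderate confidence.

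**What to change.** In Section 11.0, Primary Objectives, replace the split sentence with: *The first 125 patients accrued in each race group form the training set and the second 125 in each race group form the validation set.*

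In Section 11.0, Secondary Objectives, state that the race-specific models and the AUC comparisons use this race-balanced split or, alternatively, all 250 men of each race with cross-validation. This second edit is needed because the first does not settle which data the race models use.

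The sets stay at 250 and 250, each half African-American and half Caucasian, with no extra patients, assays or visits. The small cost is that each race moves from training to validation on its own date, so the calendar periods of the two sets may overlap across races.
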